6.2.1.1. Procedure: NO IMMEDIATE RISK

If it is clear to you that the participant poses no immediate risk to herself (i.e., the participant is not currently suicidal, but alluded to self-harm for some other reason, for example, to express how difficult their life circumstances are), then you should do the following:

- Complete the appointment,
- Remind participant of limits to confidentiality from the "Participant Information and Consent Form" and discuss seeking help by contacting LifeLine, SADAG or the Mental Health Nurse,

c) After following these steps, you should complete an incident report form and report the incident to the Project Coordinator. Chapter 7 describes the reporting process in more detail.

6.2.1.2. Procedure: IMMEDIATE RISK

If you assess that the participant is at **immediate risk** to herself, read the following script to the participant:

Script: Risk of participant suicide or self-injury (immediate danger of harm)

Team member reads:

"When you agreed to participate in this study, I promised that I would tell someone what you told me only if it was necessary to protect you or other people. You told me earlier that you were thinking of harming yourself. I suggest we contact an organization called LifeLine or SADAG and let them know so they can talk to you about how you feel. LifeLine and SADAG offers counseling. You can discuss your problem with one of their counsellors and they may be able to help you. Do you want to call them, or should I call them for you?"

Willing participant:

- If the participant agrees to contact Lifeline or SADAG, use the project phone to make the call for the participant, hand them the phone and go to another room to give them privacy during the call.
- If the participant asks you to make the call on their behalf, use the project phone to make the call for the participant, hand the phone to the participant and go to another room to give them privacy in the call.

Unwilling participant

- If the participant is unwilling to contact the crisis hotline and doesn't want you to contact them, then you should immediately contact the Project Coordinator/Site PI, who can assess the situation (e.g., determine reasons why the participant is unwilling to contact the hotline so these issues can be addressed) and who can contact one of the psychologists in the investigative team for further inputs.

- You can also contact the family physician and/or mental health nurse at the facility for their guidance.
- In the meantime, do not leave the participant by herself nor let them leave on their own, as they pose a risk to themselves.
- Ask the participant if she has a close family member or friend who can come to sit with them until you receive clear instructions about what to do.
- If the participant remains unwilling to contact the hotline, provide the participant with the referral guide as well as the counselling hotline numbers.
- Make sure you document who you spoke to, and the advice provided on the incident form (see Chapter 7)

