6.1. What is a distressed participant?

By “distressed” we mean that a participant shows signs of experiencing negative emotions and by her words, expressions, or other nonverbal behaviors or body language indicates that she is emotionally upset.

Possible signs or indications of distress:

- A participant who is tearful and/or reports that she feels badly or is sad.
- A participant who shows signs of being considerably more nervous or anxious (e.g., very nervous speech, increased sweating, difficulty sitting still during the appointment) than would be expected during an appointment.
- A participant who seems agitated or aggressive and that you cannot easily calm down.

6.1.1. Steps to follow with mildly distressed participants who need additional services.

In most cases of distress, participants may talk about feeling badly but you will be able to manage or contain these feelings and continue with the appointment. They may, however, need additional services or support once all study appointments have been completed.

In these cases, complete the following steps at the end of the study appointment:

- Indicate to the person that they seem upset or anxious.
- Discuss with the participant the importance of additional support.
- Ask if they would like to receive additional services to talk more about feelings that came up during the course of the study.

- If the participant indicates she would like to talk with someone further, ask if they would like you to refer them to an organization.
- Complete the referral and release form.
- With the patient's permission, call the agency or the mental health nurse to make an appointment.
- Provide the patient with a copy of the referral letter in an envelope and keep one in the CONTACTS folder.
- Provide the patient with a copy of our resource guide for additional services.
- If the participant indicates that she does not want you to make a direct referral, suggest various organizations for her to contact on her own and give them a copy of the resource guide.

These steps should only be followed if the participant shows signs of distress or expresses a need for further support - but **no suicidal intent or imminent harm is disclosed or suspected.**

If the person expresses any desire to end their life or hurt themselves or others, follow the steps described in 6.2.

6.1.2. Steps to follow with very distressed participants.

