There may be instances where participants are so distressed that you are concerned for their safety and may not be able to continue with the appointment. Remember that we have made it clear in the consent form that there are exceptions to our promise of confidentiality. If participants express the intent to harm themselves or others, or ongoing abuse and/or neglect of children, then we have a duty to report this matter to the proper authorities, e.g., the police, courts or social workers. Field staff will provide information on toll-free hotlines that people can call to talk to someone and seek assistance, as well as local resource information.

If during the study you are concerned that a participant intends to harm herself or others, then mandatory reporting procedures need to be followed on completion of the appointment. Immediately inform the Project Coordinator and the Site PI, who will report the mandatory reporting incidents to the ethics committee and our project officer within 72 hours.

In these instances, please follow the following steps:

- As far as possible, complete the study appointment.
- Indicate to the person that they seem upset or anxious.
- If they are expressing a desire to end their life (suicide), explore further whether this is an expression of distress or whether they have a) had previous attempts, b) have a plan to end their life.
- If there is immediacy and a plan for suicide, remind the person of the limits of confidentiality as expressed in the consent form, and your duty to report.
- Follow the mandatory reporting procedures described below.
- Complete the referral and release form
- Call the the mental health nurse to make an immediate appointment or accompany the participant to the ER section of the healthcare facility.
- Provide the patients with a copy of the referral letter in an envelope and keep one in the CONTACTS folder.
- Provide the patient with a copy of our resource guide for additional services.
- Follow the reporting procedures in Chapter 7- complete an incident report form and immediately send to the Project Coordinator and Site PI who will both keep copies on file.

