6.2.2.2. IMMEDIATE RISK

If immediate danger is perceived, please alert the Project Coordinator and the Site PI immediately and they will report the incident to the authorities. Do not let the participant leave before you have instructions from the police as to the next steps to take. Please follow each of these steps. If you feel in danger, please follow the safety procedures outlined in the manual and ask for the assistance of the clinic's security personnel.

It is highly unlikely that you will be faced with this situation!

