7.2. Identification and Initial Reporting of Incidents

The study depends upon staff to identify and report incidents promptly so that management can know about issues and respond appropriately. When study staff believe they have witnessed, experienced or learned of an event that fits the definition of an incident (AE or SAE), they should verbally report it immediately to the Project Coordinator. The staff member and the Project Coordinator will discuss the incident and if they agree it meets the definition of an incident, the Project Coordinator will provide guidance to the staff member, if needed, to complete, sign and submit the **Incident Report Form**.

In the case that an incident poses a threat to a staff member, the staff member should remove themselves from the threat according to safety procedures. If participants experience any adverse reactions to the intervention part of the study, the staff member will contact the Project Coordinator and/or Site PI immediately for additional support. Based on advice from senior project staff, the field staff will make recommendations for appropriate referrals to medical, counselling and/or other health services.

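### Section 6.2.1.2 sends the fieldworker out of the room when a participant at immediate suicide risk accepts the hotline call, but forbids leaving her by herself if she declines, although the stated reason applies to both

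*Protocol*

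**What the plan says.** Section 6.2.1.2 of the Protocol begins once the fieldworker has assessed a participant as at immediate risk to herself. The script she then hears is headed "Script: Risk of participant suicide or self-injury (immediate danger of harm)". It offers a call to one of two counselling lines, and the procedure splits on her answer.

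- **Willing, agrees to contact the line.** The fieldworker places the call on the project phone and is told to "hand them the phone and go to another room to give them privacy during the call".
- **Willing, asks the fieldworker to call for her.** The fieldworker places the call and is told to "hand the phone to the participant and go to another room to give them privacy in the call".
- **Unwilling.** The fieldworker contacts the Project Coordinator or Site PI and may consult the family physician or mental health nurse. Meanwhile the instruction is "do not leave the participant by herself nor let them leave on their own, as they pose a risk to themselves". The fieldworker also asks whether a relative or friend can come and sit with her.

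The willing branch names nobody to stay with or watch the participant, has no rule about her leaving, and gives no step for after the call.

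**The concern.** The two branches give opposite supervision instructions for women who have received the same risk assessment. The rule against leaving the participant by herself is justified by the danger she poses to herself, not by her refusal of the call. That danger is what brought her into the section, so the same reasoning should protect the woman who accepts.

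Accepting is also the response the script is designed to obtain. A fieldworker who follows the text literally therefore gives less physical protection in the outcome the procedure is aiming for. What is at stake is participant safety during the call. No endpoint, estimate or analysis in the SAP is involved.

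**Working it through.** No arithmetic bears on the inconsistency itself. The check sets the relevant provisions side by side and looks for any text that resolves the difference.

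**1. Is the entry condition shared?** Yes. Section 6.2.1 separates immediate from non-immediate risk, and 6.2.1.1 deals with the latter. Both branches of 6.2.1.2 sit under the immediate-risk heading and follow the same script.

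**2. What does each branch require?**

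| | Willing (both bullets) | Unwilling |
|---|---|---|
| Fieldworker's position | Another room | With the participant |
| Rule against her leaving alone | None | Yes |
| Companion sought | No | Yes, relative or friend |
| Reason given | Privacy | Risk to herself |

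Both of the two willing bullets send the fieldworker out.

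**3. Is risk reassessed between acceptance and the fieldworker leaving?** No such step appears. Under 6.2.1, suicidal thoughts without a plan do not count as immediate risk, and staff are asked to explore access to means. A woman who reaches 6.2.1.2 may therefore have both a plan and the means.

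**4. Does another section supply supervision during the call?**

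- Section 6.1.2 calls for an immediate mental health nurse appointment, or for staff to "accompany the participant to the ER section of the healthcare facility". It also requires immediate notification and an incident form. These steps do not depend on willingness to call, but they do not cover the call itself or override the instruction to leave the room.
- Section 7.2 says of staff who learn of an incident that "they should verbally report it immediately to the Project Coordinator". That is reporting, not supervision.
- The advice in Chapter 4 on data collection problems (section 3.1) to alert medical staff about an unwell participant is general and assigns nobody to stay.

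**5. Is the fieldworker expected to use judgement instead?** Section 6.2 presents the mandatory procedures as relieving staff of having to decide for themselves. That favours reading 6.2.1.2 literally.

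**6. How many participants could be affected?** The introduction to Chapter 5 plans 30 pregnant and 30 post-partum women, so the ceiling is 30 + 30 = 60. Section 5.2 excludes women with current suicidal thoughts, or attempts in the past month, so the actual number should be far lower. The documents give no expected rate. The exclusion applies at screening, whereas section 5.4 provides for twice-weekly urine monitoring and follow-up assessments at 6 weeks and 3 months. Section 7.1.1 lists suicidal ideation among possible adverse events, and 7.1.2 describes participants as at risk of postpartum depression and clinical worsening. The protocol itself thus allows for cases arising after enrolment.

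**Two side points of little weight.** First, for immediate risk to others, section 6.2.2.2 says "Do not let the participant leave before you have instructions from the police as to the next steps to take" without further condition. This shows that the authors could write a blanket rule, but it concerns leaving the premises, and that procedure has no hotline offer to accept or decline. Second, section 6.1.1 redirects staff with "If the person expresses any desire to end their life or hurt themselves or others, follow the steps described in 6.2", and the willing branch does not point back to 6.1.2. The 6.1.2 steps still apply, so no reporting gap follows.

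**The case against.** The strongest reply is that the branches differ in a way that matters. The fieldworker places the call before handing over the phone, so the willing participant is in contact with a crisis counsellor when the fieldworker steps out. The unwilling participant has no such contact, and her no-leave rule is tied to the wait for advice from senior staff. Privacy may help a distressed woman speak openly, and less of it could discourage her from calling. On this view the difference is a deliberate trade-off. It lasts for one call, and the nurse or ER step follows.

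It is also fair to say that the text never states that she is alone. That is inferred from the instruction to leave with no replacement named. The willing branch does not tell staff to let her leave the facility either.

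These arguments limit the point without removing it. A counsellor on the phone cannot stop her acting or walking out. The wait for advice sets how long the no-leave rule lasts, but the reason given for it is her risk. Privacy of conversation requires the fieldworker to be out of hearing, not out of sight. The inference that nobody stays is the natural reading of an instruction to go to another room. What does stand is that the exposure is brief, the cases will be few, and the balance between privacy and observation is partly a clinical judgement.

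**Conclusion.** The concern holds. Section 6.2.1.2 states a reason for not leaving an immediate-risk participant by herself, and then directs the fieldworker away from her in both willing bullets without naming anyone to stay. The protocol should be changed.

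The affected group is every participant assessed as at immediate risk who accepts the call: at most 60 and probably very few, each for the length of one call. The possible harm per event is serious injury or death. The conclusion rests on reading the instruction literally and on the absence of any other person assigned to remain. It implies no failure of adverse event capture and no effect on any analysis.

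**What to change.** 1. Move the rule against leaving the participant by herself or letting her leave on her own from the unwilling branch to the head of 6.2.1.2, so that it covers every immediate-risk case.
2. In both willing bullets, replace the instruction to go to another room with staying within sight but out of earshot. Have the psychologists on the investigative team confirm the wording.
3. As a convenience, add one line to the willing branch: after the call, follow 6.1.2 (nurse or ER, immediate notification of the Project Coordinator and Site PI, incident form).

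The cost is one rule moved, two bullets reworded, one line added and a short retraining note, with the documentation and ethics approval that Chapter 4 (Potential Improvements) attaches to protocol changes. The same fieldworker stays, so no extra staff are needed, provided the rooms allow sight without hearing. The documents do not describe the rooms, so each facility should check this. The price to the participant is slightly less privacy during the call. Data collection and the SAP are unchanged.

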6.2.2. Hurtful Intent to Others

It is extremely unlikely, but someone may spontaneously tell you that they are planning to seriously hurt or kill someone else. If a participant expresses an interest in harming or killing someone else, you should take the following steps.

- As far as possible, complete the study appointment.
- Indicate to the person that they seem upset.
- If they are expressing a desire to hurt someone else, explore whether there is an immediate risk (i.e., they have a plan and the means to do it).
- If there is immediacy and a plan, remind the person of the limits of confidentiality as expressed in the consent form, and your duty to report.
- Follow the mandatory reporting procedures described in Chapter 7.
- Complete an incident report form and immediately send to the Project Coordinator and Site PI who will both keep copies on file.

6.2.2.1. NO IMMEDIATE RISK

If no immediate danger is perceived, advise the Project Coordinator and the Site PI immediately who will evaluate the seriousness of the issue and give advice on what to do. If the danger of harm is definitely credible, then the authorities will be called to report the incident. If the danger of harm is believed to definitely be credible, you may be advised to contact the police.

6.2.2.2. IMMEDIATE RISK

If immediate danger is perceived, please alert the Project Coordinator and the Site PI immediately and they will report the incident to the authorities. Do not let the participant leave before you have instructions from the police as to the next steps to take. Please follow each of these steps. If you feel in danger, please follow the safety procedures outlined in the manual and ask for the assistance of the clinic's security personnel.

It is highly unlikely that you will be faced with this situation!

6.2.3. Child Abuse/Neglect

It is extremely unlikely, but someone may tell you that s/he has abused or neglected a child. If a participant reports this, you must report the incident to the police (if sexual abuse), or Childline (if any other type of abuse) after completing the appointment.

Follow these steps:

- As far as possible, complete the study appointment.
- Indicate to the person that they seem upset.
- If they are reported abusing a child, remind the person of the limits of confidentiality as expressed in the consent form, and your duty to report.
- Follow the reporting procedures in Chapter 7- complete an incident report form and immediately send to the Project Coordinator and Site PI who will both keep copies on file.

CHAPTER 7: INCIDENT REPORTING

7. Introduction

This chapter will outline the various types of reporting that may take place, and under which circumstances they should occur.

Although the proposed study presents no greater than minimal risk to participants, adequate provisions to mitigate these risks will be outlined further in this chapter.

The potential risks to participants include:

- 1) lack of comprehension and acknowledgement of informed consent, study purpose, and rights of participants;
- 2) exposure to psychological or physical coercion by clinical staff and others;
- 3) possible disclosure of confidential information;
- 4) the possible mental discomfort associated with some of the sensitive issues raised during assessments and biological specimen collection and results; and
- 5) social ramifications of participation in the study.

7.1. **Incident Reporting**

Incidents are defined as untoward events that occur during conduct of research projects and that affect research participants or staff or may affect study progress.

It is the responsibility of study staff who becomes aware of incidents to report them promptly so that they can be evaluated, reported and responded to appropriately by the study management. Depending on what has occurred, a reported incident may also qualify as an adverse event (AE) or serious adverse event (SAE), social harm, protocol deviation, and/or require reporting to civil authorities.

Examples of incidents that might occur during the study and should be reported include:

- a participant becomes violent towards a staff member.

- a participant reports to a fieldworker that she has suffered abuse from her husband because of her participation in the study or intervention.
- a staff member learns of distrust or rumours spreading about the study in the community,
- a staff member commits or becomes aware of a breach of confidentiality or a lapse in ethical conduct by staff,
- protests / strikes / riots in the community that affect the work of fieldworkers.
- occupational health hazards such as occupational TB,
- a staff member becomes aware of child abuse in the home

These and other incidents should be reported to the study management who will collate and triage all reports, and, depending on the category of incident, report to the study PIs, funders and regulatory bodies.

7.1.1. Adverse Events (AE)

Adverse Events (AEs) will be defined as: report of coercion to participate in the study; or significant hesitation, concern or emotional distress from answering research, such that the participant decides to stop their participation; and harm resulting from breach of confidentiality. Medical events for postpartum health, psychiatric issues including suicidal ideation, or substance abuse that do not require urgent medical attention, emergency care, and/or hospitalization will be also treated as AEs. We will monitor attrition rates for participants but drop out from the study will not be reported as an AE unless it is decided to be related to an untoward event from study participation. Clinically insignificant events are not considered AE's. Examples of clinically insignificant events include mild viral illness (e.g., colds, flu, and runny nose), common headaches, minor scratches, and mild symptoms or problems associated with medical conditions not related to the postpartum periods. As per the definition of AEs, only significant worsening of baseline medical or psychiatric status or new problems will be reported as AEs.

